## 9.3. Statistical Analyses

### 9.3.1. General Considerations

All study data will be summarized using descriptive statistics. Categorical variables (eg, race, ethnicity) will be reported as frequency and percent. Continuous variables will be reported as number of participants, mean, SD, median, minimum, and maximum (eg, age, weight). All summaries, statistical analyses, and individual participant data listings will be completed using SAS software (SAS Institute, Inc.; Cary, NC), version 9.3 or later.

#### 9.3.1.1. Definition of Study Periods for Analysis

Day 1 is defined as the first day of XYWAV use. The Screening Period includes all measurements taken after informed consent is obtained until Day 1. Baseline refers to the most recent observation prior to Day 1. The Intervention Period extends from Day 1 until the EOT Visit or the E/D Visit (whichever is earlier).

Windows for “daytime” and “nighttime” will be designated by the participant per their reported sleep and wake times in the sleep diary on the days that the ambulatory BP monitors are used. Supporting analyses will use fixed time windows for “daytime” and “nighttime” periods as defined in the SAP.

### **9.3.1.2. Intercurrent Event Strategies**

The following intercurrent events may occur during the study:

- Study intervention discontinuation due to AEs, lack of efficacy, or use of other (prohibited) concomitant medications, etc.
- Withdrawal from the study
- Lost to follow-up
- Change in antihypertensive drug use during the Intervention Period

A Treatment Policy strategy will be used for each specified analysis (ie, the data will be collected and analyzed regardless of whether an intercurrent event has occurred). Participants who do not experience certain intercurrent events while on study (eg, change in antihypertensive drug use) will be included in a sensitivity analysis.

If a participant discontinues the study intervention before the scheduled EOT Visit, then the participant’s 24-hour ambulatory SBP data will be collected as soon as possible. Missing assessments after discontinuation of study intervention due to an AE, lack of efficacy, or any other reason will not be imputed for the primary analysis.

### **9.3.1.3. Pooling of Investigational Centers**

Data from all investigational centers will be pooled for analyses of all endpoints. Data may also be pooled by region as appropriate for exploratory analyses.

### **9.3.1.4. Dropouts and Missing Data**

Subject to satisfactory data capture throughout the 24-hour period, device-estimated summaries of total, daytime, and nighttime BP measurements will be used where possible. Repeated 24-hour ambulatory measurement is permitted if satisfactory data are not acquired.

All reported data will be included in the summaries without imputation of any missing data.

### **9.3.2. Primary Endpoint**

The primary estimand is described in Section 3. The 24-hour average SBP will be calculated as the average of all ambulatory SBP measurements during the specified 24-hour window.

The primary hypothesis is that the decrease in 24-hour average SBP is statistically significant 6 weeks after switching from twice-nightly high-sodium oxybate to XYWAV.

$$H_0: \Delta_{SBP} = 0; H_1: \Delta_{SBP} < 0$$

$\Delta_{SBP}$  is the difference in the 24-hour average SBP from baseline to EOT, which will be estimated from an analysis of covariance model of the change from baseline as the dependent variable and

mean-centered baseline value as a fixed effect. In addition, 95% confidence intervals will be provided.

Mean centering of baseline values is performed for computational convenience and replaces the observed baseline value in the model ( $X_i$ ) with  $(X_i - X_{\text{mean}})$ , where  $X_{\text{mean}}$  is the estimated mean baseline value in the sample (Barnett, 2005). The resultant model is mathematically equivalent to an “observed value” baseline adjustment model, except that the model intercept term is estimated at the sample mean baseline value rather than at zero.

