#### 9.1.1. Multiplicity Adjustment

To address the multiplicity issue due to multiple endpoints, a fixed hierarchical testing sequence will be employed. The formal testing procedure will stop when a  $P$  value exceeds the prespecified significance level. Statistical significance for the primary endpoint will be assessed using O'Brien-Fleming alpha levels of 0.00998 at the interim analysis. If the primary endpoint is met at the interim analysis, study enrollment will end and the primary endpoint will not be tested again (see Section 9.4). If the primary endpoint is not met at the interim analysis, study enrollment will continue and the O'Brien-Fleming alpha level of 0.02194 will be used for the final analysis.

The secondary endpoints will be tested only once – at the interim analysis if the primary endpoint is met at the interim analysis, or at the final analysis if the primary endpoint is not met at the interim analysis but is met at the final analysis. In group sequential designs with hierarchical endpoints, typical alpha recycling methods do not conserve the family-wise error rate, and separate error spending functions for primary and secondary endpoints are suggested (Glimm, 2010). For studies in which O'Brien-Fleming alpha levels are used for testing the primary endpoint, the use of Pocock alpha levels for testing secondary endpoints is recommended (Glimm, 2010). Therefore, statistical significance for each of the secondary endpoints will be assessed using the Pocock alpha level of 0.0168 when assessed at either the interim or final analysis.

Statistical hypotheses to be tested (in sequential order):

1. Change in the 24-hour average SBP (mm Hg) following 6 weeks of XYWAV treatment after switching from twice-nightly high-sodium oxybate in participants with narcolepsy
2. Change in the daytime average SBP (mm Hg) following 6 weeks of XYWAV treatment after switching from twice-nightly high-sodium oxybate in participants with narcolepsy
3. Change in the seated resting average SBP (mm Hg) following 6 weeks of XYWAV treatment after switching from twice-nightly high-sodium oxybate in participants with narcolepsy

4. Change in the nighttime average SBP (mm Hg) following 6 weeks of XYWAV treatment after switching from twice-nightly high-sodium oxybate in participants with narcolepsy

Other endpoints will be handled in an exploratory manner and will not be involved in multiplicity adjustment.

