## 9.4. Interim Analysis

A 2-stage group sequential design with sample size re-estimation is used for this study. An interim analysis will be performed after 43 participants (75%) have completed the study. This interim analysis will include a binding stopping rule for efficacy if the primary endpoint (specified in Section 3) is met. Using the sample size assumptions described in Section 9.5, the

calculated O'Brien-Fleming alpha level for statistical significance on the primary endpoint is 0.00998 for the interim analysis.

If the primary endpoint does not reach the necessary significance level for early termination at the interim analysis, study enrollment will continue and the final sample size will be adaptively determined using a “promising zone” approach (Mehta, 2011). Based on the observed effect size at the interim analysis, the conditional power (ie, probability of reaching statistical significance at the final analysis given the data obtained at the interim) for the primary endpoint will be calculated. Because the Type I error probability is not inflated when using conditional power and the promising zone methodology used in this study to determine the situations in which the sample size can be increased (Mehta, 2011), no further adjustment to the O'Brien-Fleming boundaries (described in Section 9.1.1) is required for the final analysis.

The conditional power is calculated as follows (Mehta, 2011, equation 6):

$$CP = 1 - \Phi\left(\frac{z_{\alpha}\sqrt{n_2} - z_1\sqrt{n_1}}{\sqrt{\tilde{n}_2}} - \frac{z_1\sqrt{\tilde{n}_2}}{\sqrt{n_1}}\right)$$

Where:

$\Phi(\bullet)$  is the standard normal cumulative distribution function

$n_1$  = actual sample size at interim analysis (expected to be  $n_1 = 43$ )

$n_2$  = planned sample size at final analysis (ie,  $n_2 = 57$ )

$\tilde{n}_2$  = sample size increment between interim and planned final analyses (expected to be  $\tilde{n}_2 = 14$ )

$z_{\alpha}$  = the standard normal value for a type I error rate of  $\alpha$ ; ie,  $\Phi(1 - 0.025) = 1.95996$

$z_1 = \bar{x}_1 / se(\bar{x}_1)$ , the z-statistic for 24-hour SBP change from baseline computed at interim analysis

Based on the calculated conditional power, one of the following 3 actions will be taken:

1. “Favorable zone”: If conditional power  $\geq 90\%$ , continue enrolling participants until the prespecified target sample size ( $N = 57$ ).

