## 9.5. Sample Size Determination

The sample size is dependent upon the results of the planned interim analysis (refer to Section 9.4). The sample size also accounts for a 60% screen failure rate after enrollment (ie, signing the ICF) during the Screening Period and assumes a 15% discontinuation/withdrawal rate during the Intervention Period. Based on these assumptions, approximately 170 (up to approximately 230) study participants will enroll to enable a minimum of 67 (up to approximately 91) to initiate the study intervention (ie, switch to XYWAV) and to capture complete data (both during the Screening Period and at the EOT Visit) for a minimum of 57 participants (up to approximately 77).

There are no historical data on 24-hour average BP changes in participants switching from twice-nightly high-sodium oxybate to XYWAV. Given the limited information, data from other studies with drugs similar to oxybate were leveraged to inform the design of this study. It was determined that an effect size of 3.0 or 3.5 with a SD range from 7.0 to 8.0 will be considered for power and sample size calculations. Sample sizes for different scenarios (different effect size and SD) were calculated ([Table 6](#)). Power calculations were performed assuming a 1-sided Type 1 error rate of 0.025.

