## 5.4. Level of Significance & Multiplicity Adjustment

To control family-wise error rate inflation due to multiple endpoints and the interim analysis (Section 3.5), a fixed hierarchical testing sequence will be employed. Testing begins with the first endpoint at the specified alpha level and continues through the sequence until an endpoint is not statistically significant. Remaining analyses will be considered exploratory and associated p-values will be considered nominal.

The Type I error rate for study endpoints will be set at a one-sided level of 0.025. To account for the possibility of ending the study at the interim analysis, statistical significance for the primary endpoint (#1) will be assessed using O'Brien-Fleming one-sided alpha levels of 0.00998 for the interim analysis and 0.02194 for the final analysis. Statistical significance for each of the secondary endpoints (#2 to #4) will be assessed using the Pocock one-sided alpha level of 0.0168 at either the interim or final analysis.

Statistical hypotheses to be tested (in sequential order):

1. Change in the 24-hour average SBP (mm Hg) following 6 weeks of XYWAV treatment after switching from high-sodium oxybate in participants with narcolepsy
2. Change in the daytime average SBP (mm Hg) following 6 weeks of XYWAV treatment after switching from high-sodium oxybate in participants with narcolepsy
3. Change in the seated resting average SBP (mm Hg) following 6 weeks of XYWAV treatment after switching from high-sodium oxybate in participants with narcolepsy
4. Change in the nighttime average SBP (mm Hg) following 6 weeks of XYWAV treatment after switching from high-sodium oxybate in participants with narcolepsy

Analyses not part of this hierarchy will be considered exploratory, and no multiplicity adjustment will be performed. P-values reported in standard table outputs will be considered nominal.

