#### **7.1.1. Primary Analysis**

An analysis of covariance (ANCOVA) model will be used to estimate the primary efficacy endpoint using the SAS PROC MIXED procedure on the Completer Set. The model will include the change in 24-hour SBP from baseline to EOT Visit as the dependent variable and the mean-centered baseline 24-hour SBP as an independent variable in the model.

$$\text{BASE\_CENTERED} = \text{BASE} - \overline{\text{BASE}}$$

Example SAS Code for the ANCOVA model is shown below:

```
proc mixed data = DSET;  
  class avisitn;  
  where avisitn = [EOT];  
  model chg = base_centered avisitn;  
  lsmeans avisitn;  
run;
```

Least-squares mean change from baseline (LS-mean), standard error (SE), 95% confidence interval, and *p*-value will be reported. Unadjusted values at each visit, including change from baseline, will also be summarized as continuous variables.

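### The single-arm ANCOVA returns the raw mean change with a standard error too small for the population mean change, so Type I error exceeds the stated one-sided 0.025 whenever baseline and change are correlated

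*Protocol*

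**What the plan says.** Protocol 9.3.2 regresses the change from baseline on the "mean-centered baseline value as a fixed effect". It explains that the centring value is the mean baseline estimated in the sample, and that the intercept therefore refers to that value. SAP 7.1.1 implements this in PROC MIXED on the Completer Set, one EOT record per participant, as "model chg = base_centered avisitn", and reports the LS-mean, SE, 95% CI and p-value. Unadjusted change is summarised but not tested. Protocol 9.3.3 and SAP 7.2.1 use the same method for the three secondary SBP endpoints.

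The null hypothesis is a zero change in 24-hour average SBP from baseline to EOT, and the estimand in Protocol Section 3 names a patient population.

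On error rates, SAP 5.4 states: "The Type I error rate for study endpoints will be set at a one-sided level of 0.025". For the primary endpoint, Protocol 9.1.1 gives "alpha levels of 0.00998 at the interim analysis" and an "alpha level of 0.02194 will be used for the final analysis"; each secondary endpoint is tested at 0.0168. Protocol 9.4 states: "An interim analysis will be performed after 43 participants (75%) have completed the study". On sample size, Protocol 9.5 states: "Power calculations were performed assuming a 1-sided Type 1 error rate of 0.025".

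**The concern.** In a randomised trial, baseline adjustment sharpens the treatment difference, and the uncertainty in the overall baseline mean cancels between arms. Here there is one arm and nothing cancels. The adjustment cannot move the estimate; it can only shrink the SE attached to it. If that SE is too small for the quantity tested, the primary and secondary tests reject too often and the confidence intervals are too narrow. These are the study's confirmatory results. Protocol Appendix 5 records that Amendment 02 changed the alpha levels because simulated Type I error was higher than expected, so the intention to hold the stated rate is explicit.

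**Working it through.** **1. The plan's own figures.** Inputs from Protocol 9.5 and 9.1.1: mean change 3.5, SD 8.0, one-sided alpha 0.025, power 90%, boundaries 0.00998 and 0.02194, looks at 43 and 57.

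- A one-sample t-test on the raw change (noncentral t) gives n = 57 with power 90.1%, and reproduces all 18 cells of Protocol Table 6. The normal approximation gives 55. The sample size therefore rests on SE = SD/sqrt(n) = 8/sqrt(57) = 1.060.
- z(0.02194)/sqrt(0.75) gives an interim level of 0.00998, and the two levels together give an overall 0.0250. The boundaries are right.

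**2. What the model returns.** Let D be the change, X the baseline, β the slope and ρ = corr(X, D).

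- Least squares with X centred at its sample mean: intercept = mean of D.
- Model variance of the intercept: residual variance/n = SD(D)² × (1−ρ²)/n.
- Sampling variance of the mean of D: SD(D)²/n.
- Missing term: β² × Var(X)/n = ρ² × SD(D)²/n. Adding it restores SD(D)²/n.

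In one simulated data set of 57, the intercept and the raw mean were both −3.12589; the model SE was 0.920 and the raw SE 1.075.

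**3. Plausible size of ρ (assumption).** The documents give neither the baseline SD nor ρ. If both visits have the same variance σ² and correlation r, then Var(D) = 2σ²(1−r) and Cov(X, D) = −σ²(1−r) = −Var(D)/2. Hence ρ = −SD(D)/(2σ).

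| Assumed baseline SD | ρ = −8/(2σ) | sqrt(1−ρ²) | Model SE at n = 57 |
|---|---|---|---|
| 12 | −0.33 | 0.943 | 0.999 |
| 10 | −0.40 | 0.917 | 0.971 |
| 8 | −0.50 | 0.866 | 0.918 |

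**4. Error rate and coverage.** Simulation with true population mean change 0, t critical values, and the sample-size rule as printed in Protocol 9.4 (maximum 77):

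| ρ | ANCOVA, looks at 43/57 only | ANCOVA, with promising-zone rule | 95% CI coverage, n = 57 |
|---|---|---|---|
| −0.33 | 0.032–0.033 | about 0.031 | about 93.6% |
| −0.40 | 0.036–0.037 | 0.035–0.036 | about 92.8% |
| −0.50 | 0.046–0.047 | 0.044–0.045 | about 91.1% |

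The one-sample t-test gives 0.025 with the two looks, 0.024 with the promising-zone rule, and 95% coverage, whatever ρ is. At ρ = 0 the ANCOVA also gives 0.025.

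A hand check at a single look agrees: 1 − Φ(1.96 × 0.866) = 1 − Φ(1.697) = 0.045.

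**5. Secondary endpoints.** At the 0.0168 level z = 2.125. With the same ρ values, a single look at n = 57 rejects with probability 1 − Φ(2.125 × 0.943) = 0.022 up to 1 − Φ(2.125 × 0.866) = 0.033. The daytime, nighttime and seated values of ρ may differ from these.

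**The case against.** The strongest defence is conditional. Given the baselines actually observed, the model SE is correct for the mean change at that sample's mean baseline, and Protocol 9.3.2 says openly that this is where the intercept is estimated. That is true, but the null hypothesis and the estimand concern a patient population. A sample whose baselines happen to run high will show a fall with no effect present, and the conditional SE ignores this.

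It is also fair that the size is unknown. At ρ = 0 there is no inflation, and larger baseline SDs shrink it: with a fixed final n of 57, SDs of 16 and 20 mm Hg give about 0.029 and 0.028. A reader can also compute the unadjusted t-test from the planned summaries, although it is not the planned test.

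Four stronger readings are tempting and are not supported:

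- *The interim statistic contradicts the final test.* Protocol 9.4 defines z1 as the mean over its standard error, "the z-statistic for 24-hour SBP change from baseline computed at interim analysis", and does not say whether that SE is raw or model-based. This is an ambiguity, not a shown conflict.
- *Mean-centring causes the error.* The protocol is right that the centred and uncentred models are equivalent. An uncentred model evaluated at the sample mean baseline gives the same SE. The cause is treating that mean as known.
- *The alpha boundaries are wrong.* They give 0.0250 for a correctly sized test.
- *The SE is always too small.* This fails at ρ = 0. Within-person variation makes a negative ρ likely, not certain.

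**Conclusion.** The concern holds. The planned SE, CI and p-value are valid only conditional on the observed baselines, and they overstate precision for the population mean change whenever ρ is not zero. The algebra and the direction are certain; the size is an assumption. Under SD of change 8, equal visit variances and baseline SDs of 12 to 8 mm Hg, overall one-sided Type I error under the two-stage promising-zone design runs from about 0.031 to 0.045 against a stated 0.025, with CI coverage between about 93.6% and 91.1%. Because the secondary tests use the same model, every confirmatory result is affected. This is separate from regression to the mean through the entry criteria, which the model does not remove either, since its estimate equals the raw mean change.

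**What to change.** In Protocol 9.3.2 and SAP 7.1.1 and 7.2.1, base the primary and secondary tests and confidence intervals on the one-sample (paired) t-test of change, that is, an intercept-only model with n−1 degrees of freedom. Keep the baseline-adjusted model as descriptive or supportive, to show how change depends on baseline. In Protocol 9.4 and SAP 3.5, state that the interim z1 uses the same unadjusted SE, since it drives conditional power and the final sample size.

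The cost is one line of SAS code plus wording. The point estimate does not change. The SE rises by about 6%, 9% and 15% relative to the model SE (1/0.943, 1/0.917 and 1/0.866), back to the value behind Table 6. Power at n = 57 stays at the planned 90.1% for alpha 0.025, or 89.0% at the final level of 0.02194, so no additional participants are needed.

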### 9.3.3. Secondary Endpoints

The secondary estimands are described in Section 3. The 24-hour daytime and nighttime average SBPs will be calculated as the average of all SBP measurements during the daytime and nighttime windows, respectively. Secondary SBP endpoints will be analyzed using the same methods as those used for the primary SBP endpoint.

### 9.3.4. Exploratory Endpoints

[REDACTED]

### 9.3.5. Safety Endpoints

The safety endpoints are described in Section 3. Descriptive analyses of safety variables will be performed using the Safety Set. Adverse events will be mapped to SOC and preferred terms using the MedDRA classification system. No formal statistical testing will be performed.

## 9.4. Interim Analysis

A 2-stage group sequential design with sample size re-estimation is used for this study. An interim analysis will be performed after 43 participants (75%) have completed the study. This interim analysis will include a binding stopping rule for efficacy if the primary endpoint (specified in Section 3) is met. Using the sample size assumptions described in Section 9.5, the

calculated O'Brien-Fleming alpha level for statistical significance on the primary endpoint is 0.00998 for the interim analysis.

If the primary endpoint does not reach the necessary significance level for early termination at the interim analysis, study enrollment will continue and the final sample size will be adaptively determined using a “promising zone” approach (Mehta, 2011). Based on the observed effect size at the interim analysis, the conditional power (ie, probability of reaching statistical significance at the final analysis given the data obtained at the interim) for the primary endpoint will be calculated. Because the Type I error probability is not inflated when using conditional power and the promising zone methodology used in this study to determine the situations in which the sample size can be increased (Mehta, 2011), no further adjustment to the O'Brien-Fleming boundaries (described in Section 9.1.1) is required for the final analysis.

The conditional power is calculated as follows (Mehta, 2011, equation 6):

$$CP = 1 - \Phi\left(\frac{z_{\alpha}\sqrt{n_2} - z_1\sqrt{n_1}}{\sqrt{\tilde{n}_2}} - \frac{z_1\sqrt{\tilde{n}_2}}{\sqrt{n_1}}\right)$$

Where:

$\Phi(\bullet)$  is the standard normal cumulative distribution function

$n_1$  = actual sample size at interim analysis (expected to be  $n_1 = 43$ )

$n_2$  = planned sample size at final analysis (ie,  $n_2 = 57$ )

$\tilde{n}_2$  = sample size increment between interim and planned final analyses (expected to be  $\tilde{n}_2 = 14$ )

$z_{\alpha}$  = the standard normal value for a type I error rate of  $\alpha$ ; ie,  $\Phi(1 - 0.025) = 1.95996$

$z_1 = \bar{x}_1 / se(\bar{x}_1)$ , the z-statistic for 24-hour SBP change from baseline computed at interim analysis

Based on the calculated conditional power, one of the following 3 actions will be taken:

1. “Favorable zone”: If conditional power  $\geq 90\%$ , continue enrolling participants until the prespecified target sample size ( $N = 57$ ).
2. “Promising zone”: If  $40\% \leq$  conditional power  $< 90\%$ , increase the target sample size to  $(43 + \tilde{n}'_2)$ , up to a maximum of 77 completers.
3. “Unfavorable zone”: If conditional power  $< 40\%$ , continue enrolling participants until the prespecified target sample size ( $N = 57$ ).

When the conditional power falls into the “promising zone”, the additional sample size required is calculated as follows (Mehta, 2011, equation 9):

$$\tilde{n}'_2 = \left(\frac{n_1}{z_1^2}\right) \left[\frac{z_{\alpha}\sqrt{n_2} - z_1\sqrt{n_1}}{\sqrt{n_2 - n_1}} + z_{\beta}\right]^2$$

Where:

$n_1$  = actual sample size at interim analysis (expected to be  $n_1 = 43$ )

$n_2$  = planned sample size at final analysis (i.e.,  $n_2 = 57$ )

$z_{\alpha}$  = the standard normal value for a type I error rate of  $\alpha$ ; ie,  $\Phi(1 - 0.025) = 1.95996$

$z_{\beta}$  = the standard normal value for a type II error rate of  $\beta$ ; ie,  $\Phi(1 - 0.10) = 1.28155$

$z_1 = \bar{x}_1 / se(\bar{x}_1)$ , the z-statistic for 24-hour SBP change from baseline computed at interim analysis

The favorable zone threshold was set to the target study power (90%; [Mehta, 2011](#)). Based on the study parameters, the unfavorable zone threshold was determined to be approximately 40% ([Mehta, 2011](#), equations 10 to 12).

Enrollment will continue while the interim analysis is being performed. To mitigate the risk of enrolling more participants than needed (ie, “overruns”), the interim analysis will be conducted using the primary endpoint only, which will shorten the time needed to perform the analysis. However, all participants meeting analysis set criteria will be included in the final study report, regardless of the adaptive sample size target.

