**Table 6: Power and Sample Size Calculations**

Effect Size	Standard Deviation	80% Power	85% Power	90% Power
3.0	7.0	45	51	60
3.5	7.0	34	38	44
3.0	7.5	52	59	68
3.5	7.5	39	44	51
3.0	8.0	58	66	77
3.5	8.0	43	49	57

A preselected target sample size of 57 completers ( $n_0 = 57$ ) will provide 90% power to detect a difference of 3.5 points in means for the change from the baseline to the EOT Visit (after 6

weeks of treatment on XYWAV) in 24-hour average SBP when switching from twice-nightly high-sodium oxybate to XYWAV, assuming an SD of 8.0 points.

After 75% of participants have completed the study, an interim analysis will be conducted. If the study does not stop early for efficacy, conditional power for the primary endpoint will be calculated, and the adaptive sample size target may be increased up to a maximum of 77 participants (refer to Section [9.4](#)).

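### The z-statistic behind conditional power and the new sample size is not tied to the ANCOVA that decides the trial: its standard error is left undefined and, read plainly, is a different one

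*Protocol*

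**What the plan says.** Protocol 9.4 and SAP 3.5 use the same definition. The quantity z1 is x̄1/se(x̄1), "the z-statistic for 24-hour SBP change from baseline computed at interim analysis", and it enters both the conditional-power formula and the formula for the additional sample size. Neither document says which standard error se(x̄1) is, and neither names a model or covariate.

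Both documents define conditional power as the chance, given the interim data, that the final analysis will be significant. For the primary endpoint that analysis is baseline-adjusted. Protocol 9.3.2 has the change "estimated from an analysis of covariance model of the change from baseline as the dependent variable", with mean-centred baseline as a fixed effect. SAP 7.1.1 says "An analysis of covariance (ANCOVA) model will be used to estimate the primary efficacy endpoint", fitted on the Completer Set, with the LS-mean, its SE and a p-value reported. No other model is given for the interim test, so by implication the ANCOVA decides at both looks.

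**The concern.** Conditional power is meaningful only for a particular test. If z1 is the mean change over its own SE and the final test is the ANCOVA, then the zone (below 40%, 40% to below 90%, 90% or more) and the target between 57 and 77 completers are worked out for a test that will not be run. An interim result could be put in the unfavourable zone and get no increase when the deciding test would call it promising. Another could be asked for more completers than the 90% target needs.

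If the ANCOVA SE was meant, the documents do not say so. The trial is open-label and single-arm with no data monitoring committee planned, so the SE that sets the final sample size should not be left to choose once interim data are available.

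**Working it through.** **Inputs from the documents.** n1 = 43 ("An interim analysis will be performed after 43 participants (75%) have completed the study"); n2 = 57 ("A preselected target sample size of 57 completers"); z_α = 1.95996 and z_β = 1.28155 (Protocol 9.4); zone limits 40% and 90%; cap 77; one-sided levels 0.00998 (interim) and 0.02194 (final). The correlation r between baseline and change is not given, so I assume |r| = 0 to 0.5 and show the range.

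**Reproducing the plan's figures.** The protocol states "Power calculations were performed assuming a 1-sided Type 1 error rate of 0.025" and that the target "will provide 90% power to detect a difference of 3.5 points in means for the change from the baseline to the EOT Visit", "assuming an SD of 8.0 points". A one-sample t-test on the change (noncentral t, one-sided 0.025, difference 3.5, SD 8.0) gives N = 57 with power 0.9008, and it reproduces all 18 cells of Table 6. A two-look O'Brien-Fleming design at information 0.75 gives z = 2.3271 and 2.0153, that is one-sided 0.00998 and 0.02194. The plan's sample size therefore rests on the unadjusted change.

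**How the two statistics differ.** With baseline centred at its sample mean, the ANCOVA LS-mean equals the raw mean change. Only the SE changes:

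SE_ANCOVA = SE_raw × √[(1 − r²)(n − 1)/(n − 2)]

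So z_ANCOVA = z_raw × √[(n − 2)/((n − 1)(1 − r²))]. At n = 43 and |r| = 0.5 the factor is √[41/(42 × 0.75)] = 1.141.

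**Raw z1 = 2.0, protocol formulas.**
- First term: (1.95996√57 − 2.0√43)/√14 = (14.797 − 13.115)/3.742 = 0.450.
- Second term: 2.0√14/√43 = 1.141.
- CP = 1 − Φ(0.450 − 1.141) = 75.5%.
- Increment: (43/2.0²)(0.450 + 1.28155)² = 32.2, rounded up to 33, so N = 76.

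**Raw z1 = 1.5.** CP = 1 − Φ(1.326 − 0.856) = 31.9%, unfavourable, N = 57.

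The same interim data on the ANCOVA scale, with the plan's constants:

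| abs(r) | z factor | raw z1 = 2.0: CP, N | raw z1 = 1.5: CP, N |
|---|---|---|---|
| as written (raw) | 1 | 75.5%, 76 | 31.9%, 57 |
| 0.2 | 1.008 | 76.7%, 74 | 33.0%, 57 |
| 0.3 | 1.036 | 80.4%, 69 | 36.5%, 57 |
| 0.4 | 1.078 | 85.4%, 63 | 42.1%, 77 |
| 0.5 | 1.141 | 91.1%, 57 | 50.8%, 77 |

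At r = 0 the factor is 0.988, so the ANCOVA z is then the smaller one. None of these interims crosses the 0.00998 level on the ANCOVA test, so all would continue. I used the protocol's denominator √(n2 − n1). SAP formula (2) is printed with √n2 − √n1, which is a separate matter.

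**Across repeated trials.** Simulation (200,000 trials per scenario, true fall 3.5 mm Hg, change SD 8, ANCOVA tests at both looks), comparing z1 from the raw SE with z1 from the ANCOVA:

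| abs(r) | zone differs* | target N differs* | mean target N, raw / ANCOVA z1* | power, raw / ANCOVA z1 |
|---|---|---|---|---|
| 0.3 | 14% | 36% | 65.4 / 64.5 | 0.927 / 0.929 |
| 0.5 | 31% | 54% | 66.0 / 64.4 | 0.946 / 0.950 |

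*Among trials that continue past the interim.

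Separate simulation runs put the zone disagreement at about 13-32% over the same range of r. For true falls of 2.5 to 3.5 mm Hg, power differs by at most 0.9 percentage points and mean target N among continuing trials by less than 2.

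**The final boundary.** The final test uses z = 2.0153, whereas the conditional-power formula uses 1.95996. Putting 2.0153 into the formula at |r| = 0.4:
- Raw z1 = 1.5 gives CP 37.8%, so the zone and N are the same as in the plan as written.
- Raw z1 = 2.0 gives CP 82.7% and N = 66.

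At |r| = 0.5 and raw z1 = 1.5 (ANCOVA z = 1.711), CP = 1 − Φ[(15.215 − 11.222)/3.742 − 0.976] = 46%, still promising.

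**The case against.** The strongest reply is that the plan never says raw. It gives only x̄1/se(x̄1), the conditional power is said to be for the primary endpoint, and the only model for that endpoint is the ANCOVA. Because the LS-mean equals x̄1, the ratio could denote the ANCOVA statistic. This stands in part: the mean over its own SE is the plain reading of the notation, but what is certain is only that the SE is unspecified.

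A reader might infer that z1 is systematically too small. The documents do not support that. They give no r, the gap is about 1% for |r| up to 0.2, and it reverses at r = 0. A reader might also take the row at |r| = 0.4 and raw z1 = 1.5 as a promising trial misfiled as unfavourable. That change of zone disappears once the real final boundary is used, because a constant that is too low raises conditional power while a raw z1 lowers it.

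It is also fair to say that average operating characteristics barely move and that z1 is not the decision statistic. Simulated type I error is nearly the same with either z1 (0.0299 raw against 0.0303 ANCOVA at r = 0.3; 0.0432 against 0.0439 at r = 0.5). The excess over 0.025 comes from the ANCOVA SE, which ignores sampling variation in baseline. That is a separate issue, and changing z1 alone does not cure it.

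What survives is that the same interim data can lead to targets up to 20 completers apart (57 or 77), and this trial is run once.

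**Conclusion.** The point holds as a gap in specification with a real effect on a single decision. Conditional power, zone and target N are not tied to the test whose success they are defined to predict. On the plain reading, the size depends on r: negligible for |r| up to 0.2, and material from about 0.3 for interim results near a zone limit or in the upper part of the promising zone. The 13-32% zone disagreement assumes a true fall of 3.5 mm Hg, a change SD of 8 and |r| = 0.3 to 0.5, and it counts only trials that continue. The documents do not support a claim of lost power, of type I error inflation caused by z1, or of a bias in one known direction.

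**What to change.** In Protocol 9.4 and SAP 3.5, define z1 as the estimate over its SE from exactly the model and analysis set used for the interim and final tests. State the sign: the alternative is a decrease, while the formulas need a positive z1, so a fall should count as positive.

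There are two consistent routes:
- Keep the ANCOVA as the test and take z1 from it. This leaves that test's own type I error excess to be dealt with separately.
- Use the mean change over its own SE both in z1 and in the tests. This matches the one-sample basis of N = 57, and in simulation it holds type I error at about 0.024.

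On either route, conditional power should use the final boundary actually applied (one-sided 0.02194, z = 2.0153), so that it is the probability it is defined to be.

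The z1 definition costs one line in each document and needs no new data; the ANCOVA is already fitted at the interim. The second route also means amending the primary-analysis text in Protocol 9.3.2 and SAP 7.1.1. The change should be made before any interim result is seen.
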